2. SPECIFIC AIMS

Aim 1. To develop a program to improve the care of Veterans with TIA or minor stroke that can be deployed nationwide. The program includes 5 components: (1) a reporting system that is based on validated electronic quality measures that allow staff to monitor the time-sensitive processes of care and outcomes of their Veterans with TIA; (2) clinical programs based on existing VHA infrastructure (e.g., a pharmacist-based TIA medication management program); (3) a staff education and training program; (4) protocols and templates for use by clinicians, nurses and pharmacists; and (5) quality improvement support including a virtual collaborative to share lessons learned across sites. We will measure users' assessment of the PREVENT program in terms of usability, complexity, and relative advantage to deliver and improve care to Veterans with a recent TIA or minor stroke. We hypothesize that we can develop and facilitate the implementation of a program to improve guideline concordant care for Veterans with a recent TIA or minor stroke that achieves a high degree of staff satisfaction.

Aim 2. To evaluate the effectiveness of an intervention program for Veterans with TIA or minor stroke against usual care. Teams at the 6 intervention sites will be given access to the intervention program in 3 waves of 2 sites per wave. The primary effectiveness outcome is the proportion of Veterans who received all of the guideline-concordant processes of care for which they are eligible referred to as the "Without-Fail" care rate. We will compare the Without-Fail

rate observed in the post-implementation phase to the baseline period. We hypothesize that the Without-Fail care rate will be improved by the intervention program.

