4.2 Aim 2 Methods (Effectiveness)

Design

This five-year stepped-wedge^{20,21} evaluation includes a total of 6 sites, where active implementation is initiated in 3 waves each of which includes 2 sites. The project involves three

[figure not shown]
phases at each of the six sites: a one year-baseline phase, a one-year active implementation phase, and a sustainability phase of at least one year in duration follows the end of active implementation.

Power and Sample Size

The six site, stepped wedge design provides >90% power to detect an improvement in the mean facility Without-Fail rate from 25% during the baseline data period to >50% during the active implementation data period. The goal for the sample size was to recruit sites with at least 50 TIA patients per year, however, power was preserved with at least 30 TIA patients per year.

The figures below provide the plots of the power calculated based on the modified formula for testing the intervention effect $H_0: \theta = 0, H_1: \theta = \theta^M$ for the intervention effect size θ^M ranging from 0.1 to 0.3 when taking account for a potential decrement in intervention effect over time γ . The plot was based on a total of 6 clusters with a cluster sample size of 30, 50 and 70, respectively. The results demonstrated that this variant of SWD generally has a reasonable power (greater than or equal to 0.90) for detecting the intervention effect when the effect size is at least 0.15 with a cluster size no less than 30. The coefficient of variation (CV) was set at 0.2, 0.4, 0.6, and 0.8 to cover a wide range of the between-hospital variation. The CV seemed to have little effect on power.

Site Selection

Sites were invited to participate on the basis the basis of demonstrated gaps in quality of care (identified using the validated eQMs). Specifically, sites were invited to participate if they had baseline without-fail rates of <50%. Invitations were sent via email to higher volume sites first and recruitment continued until 6 participating sites were identified. No minimum threshold on volume was employed because our goal was to include sites which were diverse so that the results might be widely generalizable across the full spectrum of VHA facilities.

Allocation of Sites to Waves

Although some stepped-wedge trials randomly assign facilities to waves, PREVENT sites were allocated to waves on the basis of the pragmatics of the ability to schedule baseline and Kick-Off meetings.

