F	1/30/2017-1/30/2018	1/31-2/1/18	2/2/2018-4/12/2018	4/13/18	5/13/18-5/12/19	5/13/19-9/30/19

Primary Aim 2 Analysis:

Descriptive Analysis: The Without-Fail care rate will be estimated at each site for each of the three periods (baseline, post-implementation, and sustainability) to exam the temporal trends in the intervention effectiveness. The 95% confidence intervals for the rates will be provided.

Statistical Models: Due to the variation of sample size across the sites and across the implementation phases, generalized mixed-effects models (GLMM) at patient level with multilevel hierarchical random effects will be developed to analyze the intervention effects on the Without-Fail care rate during the post-implementation period and sustainability period compared with the baseline period.

The baseline data period is the one-year prior to the date of the baseline site visit. The active implementation phase data period extends for one year from month 2-13 after the Kick-Off event. For the primary effectiveness analysis, the main comparison is the mean facility Without-Fail rate across the six sites during the baseline data (control) period (blue shading above) versus the mean facility Without-Fail rate across the six sites during the post-implementation data period including the active implementation and one year after the active implementation phases (green and pink shadings above). We propose to model the “Without-Fail” care rate by

$$\log \frac{P(Y_{ij,k} = 1 | X_{ij,k}, Z_{ij,k}, W_{ij,k})}{1 - P(Y_{ij,k} = 1 | X_{ij,k}, Z_{ij,k}, W_{ij,k})} = \mu + \alpha_i + \beta_j + X_{ij,k}\theta + Z_{ij,k}\gamma + W_{ij,k}^t\tau$$

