where i indexes the site ($i = 1, 2, 3, 4, 5, 6$); j the implementation phase (1: baseline period; 2: active implementation phase; 3: one year after the active implementation phase); k the encounter at the i^{th} site and the j^{th} phase ($k = 1, 2, \dots, n_{ij}$); n_{ij} is the total number of encounters at the i^{th} site and the j^{th} phase; $X_{ij,k}$ and $Z_{ij,k}$ the indicators of the active implementation phase and one year after the active implementation phase, respectively; $W_{ij,k}$ the vector of the k^{th} encounter's characteristics at the i^{th} site and the j^{th} phase that could include the site characteristics; $Y_{ij,k} = 1$ the indicator of observation of “Without-Fail” care process on the k^{th} encounter at the i^{th} site and the j^{th} phase. For this model, μ represents the average log odds of Without-Fail care across the 6 sites at baseline; θ the log odds ratio between the active implementation phase and the baseline indicating the intervention effect during the active implementation phase; and γ the log odds ratio between one year after the active implementation phase and the baseline indicating the intervention sustainability effect post the implementation; α_i and β_j are the site and phase specific random effects that are assumed to be multivariate normal. After fitting the model, the normal theory can be applied to test the intervention effect at the active implementation phase and the intervention sustainability effect.

Secondary Aim 2 Analyses: Several secondary effectiveness analyses are planned.

Comparison to Matched Controls

Six control sites will be matched to each of the six PREVENT active implementation sites on the basis of: TIA patient volume, facility complexity (i.e., teaching status, intensive care unit level), and quality of care (measured by the without-fail rate). The total number of control sites will be 36. The definition of the baseline period (the specific start and end dates of the one-year baseline period) for each matched control site will be identical to the definition used for the PREVENT active site to which the controls are matched. We will compare changes in quality and outcomes at control sites to changes at PREVENT sites as a method for assessing temporal trends.

Changes in Individual Processes of Care

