An examination of the care rate of facility process for each of the seven primary processes of care across the six sites from the baseline period to post-implementation period will be conducted using the same analytical template as outlined for the primary analysis. A single risk adjustment model will be developed for use in evaluating the seven processes of care and will focus on baseline patient characteristics as follows:

Process	Risk Adjustment Variable
Anticoagulation for atrial fibrillation	Past history of atrial fibrillation (versus new afib)

	Use of anticoagulation prior to index event PMH of GI or intracranial hemorrhage Age Dementia
Antithrombotics	PMH of CAD, MI PMH of diabetes Anti-platelet or anticoagulant prior to index
Brain imaging	PMH of stroke or TIA
Carotid artery imaging	PMH CEA or stent PMH of PVD
High or moderate potency statin	Use of statin prior to index event PMH of CAD, MI PMH of diabetes History of intracranial hemorrhage LDL-cholesterol Age
Hypertension control	Kidney disease, dialysis PMH diabetes PMH of CAD, MI Antihypertensive meds before index event BP before the event and at discharge Homeless PCP visit
Neurology consult	Neurology FTE
General	Hospice, comfort care, AMA Admitted versus ED Transferred into or out of our facility Nights/weekends presentation

90-Day Recurrent Stroke Rate

(1) The 90-Day recurrent stroke rate will be estimated at each site before (baseline and pre-implementation phase) and after (active implementation phase and one year after the active implementation phase) the intervention to examine the temporal trends in intervention effectiveness for reducing the 90-day recurrent stroke rate. The 95% confidence intervals for the rates will be provided.

(2) The similar GLMM at patient level as described for the primary analysis will be developed for the incidence of 90-day recurrent stroke across the six sites and the whole study period to study the mean change of this rate. For this model, the indicator of Without Fail care at the encounter level will be incorporated into the model as the main exploratory variable to examine if the improvement of the Without Fail care rate will result in significant reduction of the 90-Day recurrent stroke rate.

90-Day Mortality

The analysis plan for the 90-day recurrent stroke rate (described above) will also be implemented for the 90-Day Mortality.

Disease-free Survival Analysis

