We will examine disease-free survival over the course of 1-year after the index event. We will use Cox proportional hazards modeling, censoring patients for either death or recurrent stroke and examine the relationship between quality of care and disease-free survival.

Temporal Trends in Effectiveness

An examination of the mean Without-Fail rate for the baseline data period through sustainability for all non-participating VA sites with at least 10 TIA patients per year. Given that Indianapolis VAMC has served as the coordinating center, we would not include that site in the analyses.

Consolidated Quality Measure

A consolidated measure of quality defined as the number of passes divided by the number of eligible patients across the seven primary processes of care will be compared for baseline versus post-implementation periods using the same approach described above for the Without-Fail rate analysis.

Secondary Processes of Care

An examination of the secondary processes of care: baseline versus active implementation data periods.

Sensitivity Analyses

The primary analysis will include the first TIA event per patient during the entire study period. In sensitivity analysis, we will include (1) the first event per period and (2) all TIA events in the analysis.

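### The primary Aim 2 model has no calendar-time term and no concurrent controls, so its intervention effect is a before-after contrast that absorbs any background trend

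*Combined protocol and SAP*

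**What the plan says.** Section 2 (Aim 2) hypothesises that "the Without-Fail care rate will be improved by the intervention program". Section 4.2 calls the design stepped-wedge. Under Allocation of Sites to Waves it discloses that "PREVENT sites were allocated to waves on the basis of the pragmatics of the ability to schedule baseline and Kick-Off meetings".

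Under Primary Aim 2 Analysis, "the main comparison is the mean facility Without-Fail rate across the six sites during the baseline data (control) period" against the same six sites' later data. The patient-level logistic mixed model is mu + alpha_i + beta_j + X·theta + Z·gamma + W·tau. Here i runs over the six sites and j over baseline, active implementation and the following year. Theta is "the log odds ratio between the active implementation phase and the baseline indicating the intervention effect during the active implementation phase", and gamma is the matching contrast for the later phase. W holds encounter characteristics and possibly site characteristics; calendar time is not named.

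Trend is addressed only among the secondary analyses:

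- **Comparison to Matched Controls** (36 sites): "We will compare changes in quality and outcomes at control sites to changes at PREVENT sites as a method for assessing temporal trends". Dates are fixed for the baseline year only; that definition "for each matched control site will be identical to the definition used for the PREVENT active site to which the controls are matched".
- **Temporal Trends in Effectiveness:** the plan will look at one further quantity, "mean Without-Fail rate for the baseline data period through sustainability for all non-participating VA sites with at least 10 TIA patients per year".

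Neither has a stated model or test, whereas several other secondary analyses refer back to the primary model.

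**The concern.** A stepped wedge separates program from calendar time through sites that are still unexposed while others are exposed, together with a time term in the model. This model has no time term. The random effect beta_j cannot stand in for one: mu, X and Z already saturate the three phases, so the data cannot separate beta_j from theta and gamma.

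Theta and gamma therefore carry any secular change in TIA care or its recording. A rising background rate would be credited to the program, and a falling one would hide a real effect. If the uncontrolled primary test and the control-site comparison disagreed, the plan does not say which governs, and the second has no model or post-period windows fixed in advance.

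**Working it through.** **Plan's own power figure.** Section 4.2 claims power of at least 0.90 for an effect of 0.15 with six clusters of 30. I take 30 as patients per site per phase-year and assume a two-sided 5% test, since alpha is not stated. A model with no time term gives SE = √(2 × 0.25 × 0.75 / 180) = 0.0456. Power is Φ(0.15/0.0456 − 1.96) = 0.908, which agrees. For 25% versus 50% with 180 per period, power is 0.999, which agrees with the stated >90%. An equal-step stepped wedge with fixed period effects gives 0.68-0.79 for 0.15 at 30. The claim thus fits a model without calendar effects, but the formula is not shown and this cannot be settled.

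**Time gaps**, from the Effectiveness Data Period Definitions table (month = 30.4375 days). Baseline-to-active midpoint gaps in months:

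| A | B | C | D | E | F | Mean |
|---|---|---|---|---|---|---|
| 23.7 | 23.9 | 15.6 | 17.7 | 16.5 | 15.4 | 18.8 |

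Baseline to sustainability (gamma) averages 29.8 months (23.7-36.5). Baseline to the pooled post period named in the main comparison averages 23.8 months (17.7-30.5).

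**Concurrent control time within the six sites.** The first post-implementation day is 8/11/17 (site A). Baseline site-days total 367 + 367 + 367 + 366 + 366 + 366 = 2,199. Those on or after that day are 13 at site E and 173 at site F, so 186/2,199 = 8.5%.

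**Bias and rejection with no program effect.** The trends are assumed; the documents give none. Bias = trend × gap/12. Rejection uses a normal approximation for two periods over six sites, without W or a positive beta_j variance. The baseline rate is 25%; ranges reflect variance at 25% in both periods or at each period's own rate.

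| Trend (points/year) | Bias in theta | Bias in gamma | P(p<0.05) for theta, 30 per site-year | P(p<0.05) for theta, 50 per site-year |
|---|---|---|---|---|
| 1 | 1.6 | 2.5 | 6% | 7% |
| 2 | 3.1 | 5.0 | 10-11% | 14% |
| 3 | 4.7 | 7.5 | 17-18% | 25-26% |
| 5 | 7.8 | 12.4 | 38-40% | 56-60% |

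For example, at 5 points and 50 per site-year: 0.078/√(2 × 0.1875/300) = 0.078/0.0354 ≈ 2.21, and Φ(2.21 − 1.96) ≈ 0.60.

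**Precision of alternatives.** These come from a linear probability model with p = 0.325, fixed site effects, separate active and sustainability effects, and six controls per PREVENT site of similar volume on identical windows. As planned at 30 per site-year, SE ≈ √(2 × 0.325 × 0.675/180) = 0.049. Power here is lower than 0.908 because the variance is taken at 0.325 rather than 0.25.

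| Model | SE at 30 | Power for 15 points at 30 | SE at 50 |
|---|---|---|---|
| As planned | 0.049 | 0.86 | 0.038 |
| Half-year effects + 36 controls | 0.052 | 0.82 | 0.041 |
| Same + pre-implementation data | 0.048 | 0.88 | 0.037 |
| Half-year effects, six sites only | 0.133-0.157 | about 0.19 at SE 0.137 | not tabulated |

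Quarter effects with controls also give 0.052.

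**The case against.** The plan does not hide its design. Aim 2 announces a before-after comparison, non-random waves are disclosed, and comparing changes at control and PREVENT sites is in words a difference-in-differences. One could say that writing down that secondary model and its dates would be enough. No trend is documented, and even the largest theta scenario, 7.8 points, is far below the 25-point target. All of that is true. It does not help the primary test, which alone carries the effectiveness hypothesis and for which the plan also claims power at 15 points.

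Some narrower points stand:

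- The rejection rates apply to a simplified model. A positive beta_j variance would widen theta's error, but it would not remove the bias.
- Parallel trends between PREVENT and control sites is a different assumption from no trend, not strictly a weaker one.
- Controls may not be wholly unexposed. The plan itself records sharing of tools and practices with other facilities, which could dilute the effect.
- Precision falls further if sites vary over time. With an assumed site-by-half-year SD of 10 points, the SE at 30 per site-year goes from 0.061 to 0.065. Power for 15 points then goes from 0.69 to 0.64, and for 25 points from 0.98 to 0.97.
- The Table 2 shell marks baseline versus active implementation as the primary period comparison and has an unadjusted p-value column, so changing the model alone would leave that p-value uncontrolled.

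**Conclusion.** The concern holds and must be fixed. As specified, theta and gamma are before-after contrasts over mean gaps of 18.8 and 29.8 months. A significant theta cannot by itself support the claim that the program improved care. The gaps and the 8.5% overlap follow directly from the plan's dates. The size of any bias depends on a trend that the documents do not give: 1 to 5 points a year would add about 1.6 to 7.8 points to theta. That is small against the 25-point target but material against the 15-point effect. The plan's 25%-to-50% power claim is not disputed.

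**What to change.** In the primary model:

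1. Add fixed calendar-time effects by half-year or quarter.
2. Include the 36 matched control sites as unexposed, over the same baseline, active and sustainability windows as their PREVENT site, and state those windows. Theta and gamma then become difference-in-differences effects.
3. Do not add calendar time to the six sites alone; site F supplies nearly all the overlap.
4. Keep the present model as supportive, and bring the Table 2 p-value into line with the new primary analysis.
5. State the parallel-trends assumption, and say how possible exposure of control sites will be examined.
6. Recompute power for the revised model.

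Optionally, include pre-implementation encounters as unexposed. Under 90-Day Recurrent Stroke Rate the plan already groups periods as "before (baseline and pre-implementation phase) and after (active implementation phase and one year after the active implementation phase) the intervention". Those encounters follow the baseline site visit, however, so some exposure is possible.

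The cost is SAP wording and a larger model; the control data are already planned. At 30 per site-year the SE goes from 0.049 to 0.052 and 15-point power from 0.86 to 0.82; 25-point power stays above 0.99. With an assumed site-by-half-year SD of 5 points, the SE goes from 0.053 to 0.056. These figures assume control volumes like those of the PREVENT sites, which the matching on volume supports.

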Aim 3. To evaluate the implementation of the intervention program across the 6 participating sites. The two primary implementation outcomes will be the number of implementation activities completed during the one-year active implementation period and the final level of team organization (defined as the Group Organization (GO Score)) for providing and improving TIA care at the end of the 12-month active implementation period. A covariate will include the degree of participation [Total # of calls attended/12 active implementation calls] in the monthly collaborative calls as noted in the call attendance. Implementation activities completed will be identified from multiple data sources: key updates and topics discussed during the collaborative calls; monthly action plan achievements and additional facilitator notes; the HUB implementation plan updates; and 6 and 12-month interviews. We hypothesize that sites that engage in ongoing [positive] implementation strategies of reflecting and evaluating, goal setting, and planning will realize the greatest implementation success (defined across the two primary implementation outcomes: number of implementation activities and the Group Organization (GO score)). We also hypothesize that sites with greatest implementation success will achieve the highest Without-Fail rate. We further plan to map implementation activities completed onto the key implementation strategies (reflecting and evaluating, goal setting, and planning) stratified by valence [positive & negative] based upon the mixed methodology coding.

Secondary Aim To evaluate the sustainability of the program. Sustainability will be evaluated over a one-year period that begins after the one-year active implementation period. We will compare the Without-Fail rate in the sustainability period to the post-implementation period. Our hypothesis is that sites that implement a facility-wide, TIA System of Care (reflected in a final 12-month GO score between 8-10) will demonstrate the greatest program sustainability as measured by the Without-Fail rate. Further, sites that maintain their implementation activities involving PREVENT-related program elements during the sustainability period will demonstrate the greatest program sustainability as measured by the Without-Fail rate.

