Aim 3 Hypothesis B: that sites with greatest implementation success (based on the number of implementation activities completed and the level of team organization for providing and improving TIA care at 12 months) will achieve the highest Without-Fail rate. The measures of implementation success will be included in the GLMM model described above as cluster-level (aka facility-level) covariates. Specifically, the change in GO score from baseline to post-implementation as well as the number of implementation activities during the active implementation phase will be included in the model along with the covariate of the number of collaborative calls attended.

Example Table: Aim 3B

Site	PRIMARY IMPLEMENTATION OUTCOMES				Final Without-Fail Rate
	Number of Implementation Activities Completed	Number of Collaborative Calls Attended	Final GO Score Provide	Final Go Score Improve	
A					
B					
C					
D					

E					
F					

Aim 3 Secondary Implementation Analyses

Example Table: Aim 3C

Strategies Used	Final Without Fail Rate	
	High	Low
Reflecting (+/-)		
Goal Setting (+/-)		
Planning (+/-)		
Facilitation Dose		
Collaborative Calls (Dose)		
Use of Hub (Data Pages)		
Clinical Champion (scale rating)		
OCAI organizational profiles		

Identification of Effective Implementation Strategies

As described above, PREVENT employs three primary implementation strategies: (1) team activation via (a) audit and feedback, (b) reflecting and evaluating, (c) planning, and (d) goal setting; (2) external facilitation; and (3) building a community of practice. In addition, PREVENT allows for local adaptation of the intervention and also takes advantage of peer pressure. The identification of successful implementation strategies will be based on a mixed methods assessment where the change in the Without-Fail rate will be used to define implementation success. As shown in Table 3C, we will compare facilities based upon a High Final Without Fail rate as defined as 50% or higher compared to those defined as low final rate (less than 50%) by the degree of engagement in implementation strategies and dose received as well as strength of clinical champion and organizational culture. Similarly, we will compare the rate of change [% of change] from baseline to end of active implementation.

External Facilitation

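### The primary GLMM puts a random phase effect on top of its fixed phase effects and has no site-by-phase random effect, so its interval does not support inference beyond the six sites if the change differs between sites

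*Combined protocol and SAP*

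**What the plan says.** Section 4.2, Statistical Models, calls for a logistic mixed model "at patient level with multilevel hierarchical random effects". The printed linear predictor is mu + alpha_i + beta_j + X theta + Z gamma + W tau. Index i runs over six sites and j over three phases (baseline, active implementation, the year after).

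- X and Z are "the indicators of the active implementation phase and one year after the active implementation phase, respectively", so theta and gamma are fixed phase effects with baseline as the reference.
- alpha_i and beta_j "are the site and phase specific random effects that are assumed to be multivariate normal".
- Testing is described thus: "After fitting the model, the normal theory can be applied to test the intervention effect at the active implementation phase". No small-sample degrees of freedom are given.

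On the target of inference, the main comparison starts from "the mean facility Without-Fail rate across the six sites during the baseline data (control) period", which points to these six sites. Site Selection in the same section says sites were kept diverse "so that the results might be widely generalizable across the full spectrum of VHA facilities".

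On variation between sites, Aim 3 (section 2) says: "We also hypothesize that sites with greatest implementation success will achieve the highest Without-Fail rate". Section 4.3 then compares sites finishing at 50% or more with those finishing lower, and also compares their rates of change from baseline. No SD of the site-specific change is given anywhere.

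**The concern.** Two features of the printed formula do not fit its purpose.

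First, three phases are already fully described by mu, theta and gamma. A random effect on the same three levels adds nothing that the data can separate from them. The model cannot be fitted as written without an unstated choice about that variance.

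Second, the term that would carry variation between sites in the size of the change is absent. X, Z and W do bear both subscripts, but X and Z vary only by phase and have coefficients common to all sites. W can absorb only what measured characteristics explain. Any remaining difference between sites in the change does not reach the standard error of theta. With six sites and a normal reference, the reported precision could be better than the data support for a statement about facilities in general.

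**Working it through.** **Inputs from the documents.** Six sites; 25% at baseline to 50%; 30 or 50 patients per site (Power and Sample Size). **Assumed.** Two-sided alpha 0.05 (not stated); SD of site-specific change in log-odds 0, 0.2, 0.3 or 0.5 (not stated); in simulations, a site-intercept SD of 0.4.

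**1. The plan's own power figure.** With 6 x 30 = 180 patients per period, a two-proportion test of 25% against 50% has power 0.999. A z test with random site intercepts gives 0.998. The >90% claim reproduces.

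**2. Duplication.** The fixed phase design has rank 3, and still 3 after the phase random-effect columns are added. In one example dataset the REML-type likelihood is flat in the phase SD (-583.831 from 0.01 to 1). The ML likelihood falls from -578.47 to -583.89, so ML moves to zero; it did so in all simulated fits. Theta stays at 1.210, but its standard error is 0.18 at a phase SD of 0.01 and 1.43 at 1.

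**3. Coverage when the phase variance is zero.** Let v = 1/(n p0 q0) + 1/(n p1 q1), with q = 1 - p, be the sampling variance of one site's change. The model uses variance v/6; for inference beyond the six sites the variance is (v + SD^2)/6. Coverage = 2 Phi(1.96 sqrt(v/(v + SD^2))) - 1.

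- n = 30: v = 1/5.625 + 1/7.5 = 0.311. At SD 0.3, sqrt(0.311/0.401) = 0.881, giving 91.6%.
- n = 50: v = 1/9.375 + 1/12.5 = 0.187. At SD 0.3, sqrt(0.187/0.277) = 0.821, giving 89.3%.

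| SD of change | n = 30 | n = 50 |
|---|---|---|
| 0 | 95.0% | 95.0% |
| 0.2 | 93.5% | 92.5% |
| 0.3 | 91.6% | 89.3% |
| 0.5 | 85.6% | 80.0% |

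Simulation of the printed model with beta_j kept, fitted by ML (1,000 trials per setting), gave 95.1/91.4/86.5% at n = 30 and 95.0/90.7/81.3% at n = 50 for SD 0/0.3/0.5.

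**4. Does significance survive at the planned effect?** Theta = ln 3 = 1.099. Dividing by sqrt((v + SD^2)/6) gives 4.2 (SD 0.3) and 3.6 (SD 0.5) at n = 30, and 5.1 and 4.1 at n = 50. All exceed 2.571, the 5-df critical value.

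**5. Smaller gains, n = 30, from 25%.** The observed follow-up rate needed for significance:

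| Test | SD 0 | SD 0.3 | SD 0.5 |
|---|---|---|---|
| z, site variation ignored | 34.5% | 34.5% | 34.5% |
| z, site variation carried | 34.5% | 35.8% | 37.9% |
| t on 5 df, site variation carried | 37.6% | 39.4% | 42.3% |

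At SD 0.3, 1.3 points come from site variation and 3.6 from the t reference.

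**6. If phase is nested in site.** With a site-by-phase effect and z intervals, simulated coverage for SD 0/0.3/0.5 is 95.7/94.5/93.2% (n = 30) and 95.5/94.0/93.2% (n = 50). Simulated type I error is 4.7-7.5% at SD 0.3 and 6.1-11.1% at 0.5. The limit when site variation dominates is P(|t5| > 1.96) = 10.7%.

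**The case against.** The strongest reply is that the formula contains an index slip. The text describes hierarchical, multivariate normal effects, which suggests phase nested in site. That reading is plausible, and the coverage table in step 3 would then not apply; the z test on six sites is only mildly anti-conservative at small SDs. What remains is that the index needs correcting and the reference distribution is still normal.

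A second reply is that the estimand is the six sites. The main comparison is worded that way, sites were invited rather than sampled, and the remark on generalizability explains the absence of a volume threshold. On that target the printed test is sound once the phase variance is zero. This stands, and is why the target must be stated.

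Third, the evidence that changes will differ is indirect. Aim 3 and the 50% cut mainly concern final levels. A common odds ratio of 3 takes baselines of 20% and 40% to 43% and 67%, on opposite sides of the cut with no variation in change. The planned comparison of rates of change is closer to the point but gives no SD. For scale only: from a common 25% baseline, three sites ending at 45% and three at 55% give an SD of 0.22; 40% and 60% give 0.44.

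A reader might infer that the printed interval is always too narrow. The documents do not support that: beta_j by itself narrows nothing, and with a positive phase variance the interval may be too wide. Nor do they support inferring that the power claim for 25% to 50% fails; it reproduces.

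The planned site-by-period rates with confidence intervals will make differences between sites visible, but they do not enter the test of theta.

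**Conclusion.** The defect in the formula is certain: the variance of beta_j cannot be estimated, and no random effect is indexed by both site and phase. Its effect on the interval is conditional. Under-coverage requires three things together: a phase variance of zero, a change that differs between sites, and inference beyond the six. Given these, coverage at 25% to 50% is about 92-86% at 30 per site and phase and 89-80% at 50, for assumed SDs of 0.3-0.5. Theta divided by its standard error is then 3.6-5.1, so the conclusion at the planned effect would usually stand. The point bears mainly on the reported precision and on smaller gains. It should be fixed, but it does not invalidate the trial.

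Aim 3B raises separate, secondary matters: three facility-level covariates are entered on six sites, and the model uses change in GO score where the hypothesis names the 12-month level.

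**What to change.** - Replace beta_j with a site-by-phase random effect and keep phase as fixed. If nesting was already meant, correct the index.
- Test theta and gamma against a t reference with about 5 df, or name a paired t on the six facility rates as the sensitivity analysis. Table 2 of the table shells already has a facility-level p-value column without naming a test.
- State whether inference is to the six sites or beyond.

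The cost is mainly wording, with some loss of precision. Intervals widen by (2.571/1.96) sqrt((v + SD^2)/v): from 1.31 at SD 0 to 1.76 (n = 30) or 2.01 (n = 50) at SD 0.5. The 5-df GLMM test is conservative when the change varies little between sites (simulated type I error 0.7-0.9% for theta at SD 0). Paired-t power for 25% to 50%, SD 0 to 0.5, is 0.97-0.82 at n = 30 and 0.998-0.90 at n = 50; this range could be set beside the existing power statement. Part of any higher significance threshold is the price of the t reference, not a fault of the printed test.
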